#### APPENDIX B STANDARDS FOR VARIABLE DISPLAY IN TLF

#### **Continuous Variables**

The precision for continuous variables will be based on the precision of the data itself. The mean and median will be presented to one decimal place more than the original results; the SD will be presented to two decimal places more than the original results; the minimum and maximum will be presented to the same precision as the original results. For model-based estimates, the results may be presented up to three decimal points, unless otherwise specified.

# **Categorical Variables**

Percentages will be presented to one decimal place. If the count is 0, the percentage will not be displayed. If the count equals the denominator, the percentage will be displayed as 100.

# APPENDIX C ANALYSIS VISIT WINDOWS FOR IMMUNOGENICITY ANALYSIS

Analysis visit windows will be utilized for immunogenicity assessments only. Data will be mapped using the following approach:

#### Step 1:

If the immunogenicity assessments are collected at a scheduled visit, the collected data will be mapped to the nominal scheduled visit, the data collected at scheduled visit will be used.

#### Step 2:

If the immunogenicity assessments are collected at an unscheduled visit, the collected data will be mapped using the analysis visit windows described in Table 5 below.

Table 5 Analysis Visit Windows for Immunogenicity Assessments

Visit	Target Study Day	Visit Window in Study Day
Day 1	1 (Date of Injection)	1, Pre-vaccination
Day 29	29	[2, 105]
Day 181	181	≥106

If a Participant has multiple assessments within the same analysis visit, the following rule will be used:

If multiple assessments occur within both scheduled visit and unscheduled visit, the assessment collected at scheduled visit will be used.

If multiple assessments occur within a given visit, the assessment closest to the target study day will be used.

If there are 2 or more assessments equal distance to the target study day, the last assessment will be used.

# APPENDIX D IMPUTATION RULES FOR MISSING PRIOR/CONCOMITANT MEDICATIONS AND NON-STUDY VACCINATIONS DATES

Imputation rules for missing or partial medication start/stop dates are defined below:

#### Missing or partially missing medication start date:

If only Day is missing, use the first day of the month, unless the start month and year of the medication coincide with the start month and year of the IP injection.

- If not marked as a prior medication on the Prior/Concomitant CRF page ("Was
  the medication taken prior to study administration?" = "No"), then use the date of
  the IP injection.
- If marked as a prior medication on the Prior/Concomitant CRF page ("Was the medication taken prior to study administration?" = "Yes"), then use the earlier of the first day of the month or the date of the IP injection 1.
- If the mark on the Prior/Concomitant CRF page ("Was the medication taken prior to study administration?") is missing and the medication end date is on/after the date of the IP injection or is missing, then use the date of the IP injection.

If Day and Month are both missing, use the first day of the year, unless the start year of the medication coincide with the start year of the IP injection.

- If not marked as a prior medication on the Prior/Concomitant CRF page ("Was
  the medication taken prior to study administration?" = "No"), then use the date of
  the IP injection.
- If marked as a prior medication on the Prior/Concomitant CRF page ("Was the medication taken prior to study administration?" = "Yes"), then use the earlier of the first day of the year or the date of the IP injection -1.
- If the mark on the Prior/Concomitant CRF page ("Was the medication taken prior to study administration?") is missing and the medication end date is on/after the date of the IP injection or is missing, then use the date of the IP injection.

If Day, Month and Year are all missing, the date will not be imputed, but will use the following rules for purposes of determining the status as prior and/or concomitant.

- If not marked as a prior medication on the Prior/Concomitant CRF page ("Was the medication taken prior to study administration?" = "No"), then the medication will be treated as having begun after IP injection.
- If marked as a prior medication on the Prior/Concomitant CRF page ("Was the medication taken prior to study administration?" = "Yes"), or if the mark is missing, then the medication will be treated as a prior medication (and as a concomitant medication unless the stop date indicates the medication was stopped prior to IP injection).

# Missing or partial medication stop date:

If only Day is missing, use the earliest date of (last day of the month, study completion, discontinuation from the study, or death).

If Day and Month are both missing, use the earliest date of (last day of the year, study completion, discontinuation from the study, or death).

If Day, Month and Year are all missing, the date will not be imputed, but the medication will be flagged as a continuing medication.

In summary, the prior, concomitant or post categorization of a medication is described in Table 6 below.

Table 6 Prior, Concomitant, and Post Categorization of a Medication

	Medication Stop Date				
Medication Start Date	< Injection Date	≥ Injection Date and ≤ Injection Date + 27 days	> 27 Days After Injection [2]		
< Injection Date [1]	P	PC	PCA		
$\geq$ Injection date and $\leq$ 27 days after injection	-	C	CA		
> 27 days after injection	-	-	A		

A: Post; C: Concomitant; P: Prior

 includes medications with completely missing start date

 includes medications with completely missing end date

#### APPENDIX E IMPUTATION RULES FOR MISSING AE DATES

Imputation rules for missing or partial AE start dates and stop dates are defined below:

#### Missing or partial AE start date:

If only Day is missing, use the first day of the month, unless:

The AE end date is after the date of injection or is missing AND the start month and year of the AE coincide with the start month and year of the injection. In this case, use the date and time of injection, even if time is collected.

If Day and Month are both missing, use the first day of the year, unless:

 The AE end date is after the date of injection or is missing AND the start year of the AE coincides with the start year of the injection. In this case, use the date of injection

If Day, Month and Year are all missing, the date will not be imputed. However, if the AE end date is prior to the date of injection, then the AE will be considered a pretreatment AE. Otherwise, the AE will be considered treatment emergent.

Missing or partial AE end dates will not be imputed.

# APPENDIX F SOLICITED ADVERSE REACTIONS AND GRADES

# Table 7 Adult and Adolescent Solicited Adverse Reactions and Grades

Reaction	Grade 0 (None)	Grade 1 (Mild)	Grade 2 (Moderate)	Grade 3 (Severe)	Grade 4 (Life- threatening)
Injection site pain	None	Does not interfere with activity	Interferes with activity	Prevents daily activity	Requires emergency room visit or hospitalization
Injection site erythema (redness)	<25 mm/ <2.5 cm	25 to 50 mm/ 2.5 to 5 cm	51 to 100 mm/ 5.1 to 10 cm	>100 mm/ >10 cm	Necrosis or exfoliative dermatitis
Injection site swelling/ induration (hardness)	<25 mm/ <2.5 cm	25 to 50 mm/ 2.5 to 5 cm	51 to 100 mm/ 5.1 to 10 cm	>100 mm/ >10 cm	Necrosis
Axillary (underarm) swelling or tenderness ipsilateral to the side of injection	None	No interference with activity	Some interference with activity	Prevents daily activity	Emergency room visit or hospitalization
Headache	None	No interference with activity	Some interference with activity	Prevents daily activity	Requires emergency room visit or hospitalization
Fatigue	None	No interference with activity	Some interference with activity	Prevents daily activity	Requires emergency room visit or hospitalization
Myalgia (muscle aches all over body)	None	No interference with activity	Some interference with activity	Prevents daily activity	Requires emergency room visit or hospitalization
Arthralgia (joint aches in several joints)	None	No interference with activity	Some interference with activity	Prevents daily activity	Requires emergency room visit or hospitalization

Reaction	Grade 0 (None)	Grade 1 (Mild)	Grade 2 (Moderate)	Grade 3 (Severe)	Grade 4 (Life- threatening)
Nausea/vomiting	None	No interference with activity or 1 to 2 episodes/ 24 hours	Some interference with activity or >2 episodes/24 hours	Prevents daily activity, requires outpatient intravenous hydration	Requires emergency room visit or hospitalization for hypotensive shock
Chills	None	No interference with activity	Some interference with activity not requiring medical intervention	Prevents daily activity and requires medical intervention	Requires emergency room visit or hospitalization
Fever (oral)	<38.0°C <100.4°F	38.0 to 38.4°C 100.4 to 101.1°F	38.5 to 38.9°C 101.2 to 102.0°F	39.0 to 40.0°C 102.1 to 104.0°F	>40.0°C >104.0°F

# APPENDIX G TOXICITY GRADING OF VITAL SIGN ABNORMALITIES

**Table 8 Toxicity Grading of Vital Sign Abnormalities** 

Vital Signs*	Mild (Grade 1)	Moderate (Grade 2)	Severe (Grade 3)	Potentially Life Threatening (Grade 4)
Fever (°C)** (°F)**	38.0 – 38.4 100.4 – 101.1	38.5 – 38.9 101.2 – 102.0	39.0 – 40 102.1 – 104	> 40 > 104
Tachycardia - beats per minute	101 – 115	116 – 130	> 130	ER visit or hospitalization for arrhythmia
Bradycardia - beats per minute***	50 – 54	45 – 49	< 45	ER visit or hospitalization for arrhythmia
Hypertension (systolic) - mm Hg	141 – 150	151 – 155	> 155	ER visit or hospitalization for malignant hypertension
Hypertension (diastolic) - mm Hg	91 – 95	96 – 100	> 100	ER visit or hospitalization for malignant hypertension
Hypotension (systolic) – mm Hg	85 – 89	80 – 84	< 80	ER visit or hospitalization for hypotensive shock
Respiratory Rate – breaths per minute	17 – 20	21 – 25	> 25	Intubation

\* Participant should be at rest for all vital sign measurements.

\*\* Oral temperature; no recent hot or cold beverages or smoking.

\*\*\* When resting heart rate is between 60 – 100 beats per minute. Use clinical judgement when characterizing bradycardia among some healthy participant populations, for example, conditioned athlete

# APPENDIX H ADVERSE EVENTS OF SPECIAL INTEREST BY SMQ

# **Table 9 Adverse Events of Special Interest by SMQ**

SMQ/CMQ Name*	Type of MedDRA Query	SMQ Level	SMQ Code	Broad or Narrow Search
Anaphylactic Reaction	SMQ	1	20000021	Algorithm
				A or (B and C) or (D and (B or C))
Angioedema	SMQ	1	20000024	Narrow
Arthritis	SMQ	1	20000216	Narrow
Cardiac Arrhythmias	SMQ	1	20000049	Narrow
Arrhythmia Related Investigations, Signs and Symptoms	SMQ	2	20000051	Narrow
Cardiac Arrhythmia Terms (including bradyarrhythmias and tachyarrhythmias)	SMQ	2	20000050	Narrow
Cardiac Failure	SMQ	1	20000004	Narrow
Cardiomyopathy	SMQ	1	20000150	Narrow
Central Nervous System Vascular Disorders	SMQ	1	20000060	Narrow
Central Nervous System Haemorrhages and Cerebrovascular Conditions	SMQ	2	20000061	Narrow
Central Nervous System Vascular Disorders, not Specified as Haemorrhagic or Ischaemic	SMQ	2	20000165	Narrow
Convulsions	SMQ	1	20000079	Narrow
Demyelination	SMQ	1	20000154	Narrow
Embolic and Thrombotic Events	SMQ	1	20000081	Narrow
Embolic and Thrombotic Events, Arterial	SMQ	2	20000082	Narrow
Embolic and Thrombotic Events, Venous	SMQ	2	20000084	Narrow
Embolic and Thrombotic Events, Vessel Type Unspecified and Mixed Arterial and Venous	SMQ	2	20000083	Narrow
Guillain-Barre Syndrome	SMQ	1	20000131	Narrow
Haematopoietic Cytopenias	SMQ	1	20000027	Narrow
Haematopoietic Cytopenias Affecting More Than One Type Of Blood Cell	SMQ	2	20000028	Narrow
Haematopoietic Erythropenia	SMQ	2	20000029	Narrow
Haematopoietic Leukopenia	SMQ	2	20000030	Narrow
Haematopoietic Thrombocytopenia	SMQ	2	20000031	Narrow
Hearing and Vestibular Disorders	SMQ	1	20000170	Narrow
Hearing Impairment	SMQ	2	20000171	Narrow
Vestibular Disorders	SMQ	2	20000172	Narrow
Hypersensitivity	SMQ	1	20000214	Narrow
Immune-mediated/Autoimmune Disorders	SMQ	1	20000236	Narrow
Ischaemic Heart Disease	SMQ	1	20000043	Narrow
Myocardial Infarction	SMQ	2	20000047	Narrow

Other Ischaemic Heart Disease	SMQ	2	20000168	Narrow
Noninfectious Myocarditis/Pericarditis	SMQ	1	20000239	Narrow
Peripheral Neuropathy	SMQ	1	20000034	Narrow
Thrombophlebitis	SMQ	1	20000115	Narrow
Vasculitis	SMQ	1	20000174	Narrow

The following criteria will be used to determine anaphylactic reaction:

A term from Category A or

A term from Category B (Upper Airway/Respiratory) and a term from Category C (Angioedema/Urticaria/Pruritus/Flush) that occurred within 24 hours of each other or

A term from Category D (Cardiovascular/Hypotension) and at least one of the following:

- A term from Category B (Upper Airway/Respiratory) that occurred within 24 hours of each other.
- A term from Category C (Angioedema/Urticaria/Pruritus/Flush) that occurred within 24 hours of each other.

Table 10 Algorithmic Approach for Anaphylactic Reaction:

Category	Scope	PT Search Term
A	Narrow	Anaphylactic reaction
A	Narrow	Anaphylactic shock
A	Narrow	Anaphylactic transfusion reaction
A	Narrow	Anaphylactoid reaction
A	Narrow	Anaphylactoid shock
A	Narrow	Circulatory collapse
A	Narrow	Dialysis membrane reaction
A	Narrow	Kounis syndrome
A	Narrow	Procedural shock
A	Narrow	Shock
A	Narrow	Shock symptom
A	Narrow	Type I hypersensitivity
В	Broad	Asthma
В	Broad	Bronchial oedema
В	Broad	Bronchospasm
В	Broad	Cardio-respiratory distress
В	Broad	Chest discomfort
В	Broad	Choking
В	Broad	Choking sensation
В	Broad	Circumoral oedema
В	Broad	Cough
В	Broad	Cough variant asthma

Category	Scope	PT Search Term
В	Broad	Cyanosis
В	Broad	Dyspnoea
В	Broad	Hyperventilation
В	Broad	Irregular breathing
В	Broad	Laryngeal dyspnoea
В	Broad	Laryngeal oedema
В	Broad	Laryngospasm
В	Broad	Laryngotracheal oedema
В	Broad	Mouth swelling
В	Broad	Nasal obstruction
В	Broad	Oedema mouth
В	Broad	Oropharyngeal oedema
В	Broad	Oropharyngeal spasm
В	Broad	Oropharyngeal swelling
В	Broad	Pharyngeal oedema
В	Broad	Pharyngeal swelling
В	Broad	Respiratory arrest
В	Broad	Respiratory distress
В	Broad	Respiratory failure
В	Broad	Reversible airways obstruction
В	Broad	Sensation of foreign body
В	Broad	Sneezing
В	Broad	Stridor
В	Broad	Swollen tongue
В	Broad	Tachypnoea
В	Broad	Throat tightness
В	Broad	Tongue oedema
В	Broad	Tracheal obstruction
В	Broad	Tracheal oedema
В	Broad	Upper airway obstruction
В	Broad	Vaccine associated enhanced respiratory disease
В	Broad	Wheezing

Category	Scope	PT Search Term
С	Broad	Allergic oedema
С	Broad	Angioedema
С	Broad	Circumoral swelling
С	Broad	Erythema
С	Broad	Eye oedema
С	Broad	Eye pruritus
С	Broad	Eye swelling
С	Broad	Eyelid oedema
С	Broad	Face oedema
С	Broad	Flushing
С	Broad	Injection site urticaria
С	Broad	Lip oedema
С	Broad	Lip swelling
С	Broad	Nodular rash
С	Broad	Ocular hyperaemia
С	Broad	Oedema
С	Broad	Oedema blister
С	Broad	Periorbital oedema
С	Broad	Periorbital swelling
С	Broad	Pruritus
С	Broad	Pruritus allergic
С	Broad	Rash
С	Broad	Rash erythematous
С	Broad	Rash pruritic
С	Broad	Skin swelling
С	Broad	Swelling
С	Broad	Swelling face
С	Broad	Swelling of eyelid
С	Broad	Urticaria
С	Broad	Urticaria papular
D	Broad	Blood pressure decreased
D	Broad	Blood pressure diastolic decreased

Category	Scope	PT Search Term
D	Broad	Blood pressure systolic decreased
D	Broad	Cardiac arrest
D	Broad	Cardio-respiratory arrest
D	Broad	Cardiovascular insufficiency
D	Broad	Diastolic hypotension
D	Broad	Hypotension
D	Broad	Hypotensive crisis
D	Broad	Post procedural hypotension

#### APPENDIX I IMMUNOGENICITY SAMPLING PLAN

# I. Random Immunogenicity Subsets for MN Assay

Random Immunogenicity Subset for MN assay consists of a random sample of approximately N=150 treated participants for each treatment arm from cohort A and cohort B respectively (i.e., approximately N=300 each cohort). A total of approximately 600 (+5% attrition rate to account for any issues regarding sample availability or participant being dropped from analysis) randomly selected participants will be sent for MN assay analysis.

A stratified random sampling method will be used to select a sample of participants for the MN assay testing. The sample of participants will be randomly drawn by unblinded team according to the treatment arm assigned and the stratification factors. The sample size from each stratum will be proportional to the number of participants in each stratum in the Full Analysis Set, to represent study population. The strata are defined based on the IRT trial randomization strata as follows:

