9.3. Sample Size Determination

With a total of 4000 participants for each cohort, approximately 2000 participants in Cohort A and 2000 participants in Cohort B (a total of 4000) will be exposed to study vaccine in the mRNA-1083 (40 μ g) + Placebo group. This will have approximately over 95% probability to observe at least 1 participant with an AE given a true 0.1% AE rate.

A subset of participants will be randomly selected from the FAS of Cohort A and B, respectively, to be tested by microneutralization assay according to the secondary objective (Section 3). Details of the sampling strategy will be documented in the SAP.

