All 4000 participants in Cohort B who meet the PPIS criteria will be included in the PPIS (in 1:1 ratio, including the assumed approximate 15% drop-outs; approximately 2000 participants receiving mRNA-1083 [40 μ g] + Placebo, and 2000 receiving Fluarix + Spikevax). This will provide at least 95% overall power to demonstrate NI across the five co-primary immunogenicity endpoints for GM level at Day 29 between mRNA-1083 (40 μ g) + Placebo and Fluarix + Spikevax in all the 4 influenza strains and 1 SARS-CoV-2 strain. The power evaluation assumes a 2-sided alpha of 0.025, approximately 15% drop-out rate, true GMR of 0.85 (SD of antibody level in natural logarithm being 1.5) and a NIM of 1.5 for GMR in all the 4 influenza strains and 1 SARS-CoV-2 strain.

The study has at least 95% overall power to demonstrate NI across the 5 coprimary immunogenicity endpoints for SCR or SRR between mRNA-1083 (40 μ g) + Placebo and Fluarix + Spikevax in all the 4 influenza strains and 1 SARS-CoV-2 strain. The power evaluation assumes a 2-sided alpha of 0.025, approximately 15% drop-out rate, an underlying SCR or SRR of 68% in the mRNA-1083 (40 μ g) + Placebo group and an SRR/SCR of 70% in Fluarix + Spikevax group (with a true SCR or SRR difference being -2%) and a NIM of 10% for the rate difference in the 2 influenza A strains and 1 SARS-CoV-2 strain, and assumes an underlying SCR of 58% in the mRNA-1083 (40 μ g) + Placebo group and a SCR of 60% in Fluarix + Spikevax group (with a true SCR difference being -2%) and a NIM of 10% for the rate difference in the 2 influenza B strains.

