9.4. Analysis Sets

For the purposes of analysis, the following analysis sets are defined:

Table 9: Populations for Analyses in Cohort A and Cohort B Substudies, Respectively

Analysis Set	Description
Randomization Set	The randomization set consists of all participants who are randomly assigned.
FAS	The FAS consists of all participants who are randomly assigned and receive the study intervention. Participants will be analyzed according to the group to which they were randomized.
PPIS ^a	The PPIS consists of all participants in the FAS who comply with the timing of immunogenicity blood sample collections to have both Baseline and Day 29 assessments, have negative RT-PCR test for influenza and SARS-CoV-2 on Day 1, and have no major protocol deviations or conditions/medications that affect the immune response.

Analysis Set	Description
PPIS for MN	The PPIS for MN consists of a subset of participants randomly sampled from the FAS to be tested for MN, who comply with the timing of immunogenicity blood sample collections to have both Baseline and Day 29 assessments, have negative RT-PCR test for influenza and SARS-CoV-2 on Day 1, and have no major protocol deviations or conditions/medications that affect the immune response.
Safety Set ^b	The Safety Set consists of all participants who are randomly assigned and receive the study intervention. Participants will be included in the treatment group corresponding to what they received.
Solicited Safety Set ^c	The Solicited Safety Set consists of all participants in the Safety Set who contribute any solicited AR data.

Abbreviations: AR = adverse reaction; FAS = full analysis set; MN = microneutralization assay; PPIS = Per Protocol Immunogenicity Set; RT-PCR = reverse transcription polymerase chain reaction; SARS-CoV-2 = severe acute respiratory syndrome coronavirus 2.

Note: Each of Cohort A and Cohort B will have its separate set of analysis populations defined as above that will be applied in separate statistical analysis planned in each of the 2 cohorts, respectively.

- a. The PPIS will be used as the primary analysis set for analyses of immunogenicity in Cohort A or Cohort B unless otherwise specified. Participants will be analyzed according to the group to which they were randomized.
- b. The Safety Set will be used for all analyses of safety, except for the solicited ARs.

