#### 4.3.1 Cohort A Substudy (≥65 Years)

Immunogenicity results from the participants in Cohort A, will contribute to the primary immunogenicity analyses for Cohort A. With approximately 2000 participants (including the assumed approximate 15% drop-outs) receiving mRNA-1083 (40  $\mu$ g) + Placebo, and 2000 receiving Fluzone HD + Spikevax, this will provide at least 95% overall power to demonstrate NI across the five co-primary immunogenicity endpoints for GM level at Day 29 between mRNA-1083 (40  $\mu$ g) + Placebo and Fluzone HD + Spikevax in all the 4 influenza strains and 1 SARS-CoV-2 strain. The power evaluation assumes a 2-sided alpha of 0.025, approximately

15% drop-out rate, true GMR of 0.85 (SD of antibody level in natural logarithm being 1.5) and a NIM of 1.5 for GMR in all the 4 influenza strains and 1 SARS-CoV-2 strain.

The study has at least 95% overall power to demonstrate NI across the five co-primary immunogenicity endpoints for SCR or SRR between mRNA-1083 (40  $\mu$ g) + Placebo and Fluzone HD + Spikevax in all the 4 influenza strains and 1 SARS-CoV-2 strain. The power evaluation assumes a 2-sided alpha of 0.025, approximately 15% drop-out rate, an underlying SRR or SCR of 68% in the mRNA-1083 (40  $\mu$ g) + Placebo group and an SRR or SCR of 70% in Fluzone HD + Spikevax group (with a true SRR or SCR difference being -2%) and a NIM of 10% for the rate difference in the 2 influenza A strains and 1 SARS-CoV-2 strain, and assumes an underlying SCR of 58% in the mRNA-1083 (40  $\mu$ g) + Placebo group and a SCR of 60% in Fluzone HD + Spikevax group (with a true SCR difference being -2%) and a NIM of 10% for the rate difference in the 2 influenza B strains.

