## 5.5 Per Protocol Immunogenicity Set for MN assay

The PPIS for MN assay will be used as the secondary analysis set for analyses of immunogenicity in Cohort A or Cohort B for influenza unless otherwise specified. Participants will be analyzed according to the treatment arm to which they were randomized.

The Per Protocol Immunogenicity Set for MN assay consists of a subset of participants randomly sampled from the Full Analysis Set to be tested for MN, who comply with the timing of immunogenicity blood sampling collections to have both Baseline (see section 6.1) and Day 29 assessments using a window of -7 to +14 days, have no major dosing error, have negative RT-PCR test for influenza and SARS-CoV-2 on Day 1, and have no major protocol deviations or conditions/medications that affect the immune response.

The major dosing error ranges, available in Table 2, will be used to determine participant exclusion from the PPIS for MN assay analysis populations.

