## 6.3.2.1 Cohort A Substudy (≥65 Years)

For the secondary and exploratory endpoints, GM level of HAI, MN or PsVNA with corresponding 95% CI will be provided at each timepoint. GMFR of HAI, MN or PsVNA with corresponding 95% CI at each post-Baseline timepoint over preinjection Baseline at Day 1 will be provided. For the influenza MN descriptive secondary endpoint GMT, an ANCOVA model will be carried out including the log-transformed MN levels at Day 29 as the dependent variable, the treatment group as the fixed variable and log transformed baseline MN levels as a fixed covariate. The model will be adjusted for the stratification factors (age group: 65 to <75 years of age and influenza vaccine status in the most recent influenza season: received or not received since September 2022). A subset of PPIS may be used for exploratory endpoints, including but not limited to immunogenicity analysis at Day 181. Descriptive summary statistics including median, Q1, Q3, minimum, and maximum will also be provided by treatment arm (available in Section 6.1). GM level and GMFR will be plotted at all evaluable timepoints.

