# 7 CHANGES FROM PLANNED ANALYSIS IN PROTOCOL

Not applicable.

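### Is the 5% allowance for the microneutralization subset too small, given the 15% drop-out assumption used elsewhere in the plan?

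*SAP*

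**What the plan says.** Protocol section 9.3 sets the sampling frame for the MN assay and leaves the details to the SAP: "A subset of participants will be randomly selected from the FAS of Cohort A and B, respectively, to be tested by microneutralization assay". SAP section 5.5 repeats the frame in defining the analysis set, which "consists of a subset of participants randomly sampled from the Full Analysis Set to be tested for MN". It then applies the per-protocol conditions: Baseline and Day 29 samples in window, no major dosing error, negative Day 1 RT-PCR for both viruses, and no major deviation, condition or medication affecting the immune response. The Full Analysis Set itself requires only randomisation and dosing (SAP section 5.2).

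Appendix I gives the size as a random sample of approximately 150 treated participants per arm in each cohort, with this reserve: "A total of approximately 600 (+5% attrition rate to account for any issues regarding sample availability or participant being dropped from analysis". Strata are proportional to their counts in the Full Analysis Set.

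The 15% figure belongs to the main sample size. SAP section 4.3.1 counts "approximately 2000 participants (including the assumed approximate 15% drop-outs) receiving mRNA-1083" and Protocol section 9.3.2 (Cohort B) says participants meeting the criteria "will be included in the PPIS (in 1:1 ratio, including the assumed approximate 15% drop-outs".

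SAP section 6.3.2.1 gives the status of the endpoint: "For the influenza MN descriptive secondary endpoint GMT, an ANCOVA model will be carried out". SAP section 6.4 leaves endpoints outside the listed tests without multiplicity control and calls their analyses descriptive.

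**The concern.** The draw is made before the per-protocol exclusions and the analysis after them, so the reserve must absorb everything lost in between. Appendix I says as much, since its 5% covers both unavailable samples and participants dropped from analysis. A proportionally stratified random sample of the Full Analysis Set should lose about the same share as the full set under the same filters. If the plan expects 15% to be lost on the way to the main immunogenicity analysis, 5% looks too small for the subset.

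At stake would be the precision of the MN geometric means, fold rises and adjusted comparisons in each cohort, and of the cross-cohort MN comparison in SAP section 6.3.2.3. A reader might also take 150 per arm as the number analysed when fewer are available.

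**Working it through.** **Inputs.** 150 per arm, two arms, two cohorts, +5% (SAP Appendix I). About 15% drop-outs, 2000 per arm, natural-log SD 1.5, true GMR 0.85, margin 0.667, two-sided alpha 0.025 (SAP sections 4.2 and 4.3). No SD is given for MN; 1.0 to 1.5 on the natural-log scale is assumed below.

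**The plan's own figure.** 150 x 2 x 2 = 600. 600 x 1.05 = 630, or 157.5 per arm. After a 5% loss, 630 x 0.95 = 598.5, or 149.6 per arm. Appendix I is consistent with itself.

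**Where the 15% is used.** 2000 x 0.85 = 1700 per arm. The standard error of the log GMR is 1.5 x sqrt(2/1700) = 0.0514, and ln(0.85/0.667) = 0.2425. Power per strain is Phi(0.2425/0.0514 - 2.241) = 99.3%. Over five strains, if independent, 0.993^5 is about 96.7%, in line with the stated 95% or more. The 15% does its job in the main calculation.

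**Loss that the reserve covers.** 1 - 150/157.5 = 4.8%.

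**Scenarios for a larger loss.** The CI width ratio is sqrt(150/n).

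| Loss, draw to analysis | Evaluable per arm | Total | Log-scale CI width against 150 |
|---|---|---|---|
| 5% | 149.6 | 598.5 | about the same |
| 10% | 141.8 | 567 | 3% wider |
| 15% | 133.9 | 535.5 | 6% wider |

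**Effect on an MN GMR.** The unadjusted 95% CI factor is exp(1.96 x SD x sqrt(2/n)). From n = 150 to n = 133.9:

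- SD 1.0: 1.254 becomes 1.271.
- SD 1.5: 1.404 becomes 1.432.

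**Draw needed for 150 at 15% loss.** 150/0.85 = 176.5, so 177 per arm. In total 600/0.85 = 706, which is 76 more than 630.

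**PsVNA cross-neutralization subset.** 60 x 1.06 x 0.85 = 54.1 per arm on the same supposition. That subset is exploratory, and SAP section 6.3 makes the per-protocol set the default for immunogenicity.

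**The case for a change.** The best case for a change is that the 15% is more than a generic planning figure. The 2000 per arm are described as receiving vaccine, and the safety calculation counts the same 2000 as exposed. Read literally, the 15% is lost after dosing, and so within the Full Analysis Set. The Cohort B text puts it in the same sentence as entry to the per-protocol set. SAP sections 6.3.1.2 and 6.3.1.4 also provide for a supplementary analysis if the per-protocol and Immunogenicity Sets differ by more than 10%. The Immunogenicity Set already requires Baseline and Day 29 results, so the plan treats a gap above 5% as possible.

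This shows that a loss above 5% is plausible and that the reason for the 5% is not written down. It does not show that the 5% is wrong:

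- Neither document calls the 15% a loss from the Full Analysis Set to the per-protocol set. The parallel Cohort A text in Protocol section 9.3.1 keeps the per-protocol sentence and the drop-out figure apart.
- The 10% trigger is a contingency, not a forecast.
- The 15% sizes the trial as a whole. The MN draw has its own rate and is made later, since its stratum sizes depend on counts in the Full Analysis Set. Appendix I was added only in SAP version 2.0.
- Appendix I words 150 as the approximate size of the random sample. Reading it as a promised evaluable number is an inference from the purpose of the reserve.

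**Conclusion.** There is no arithmetic error. The two rates belong to different steps, and 134 per arm is a scenario that needs the full 15% to apply after the draw. Even then the cost is intervals about 6% wider on a descriptive endpoint with no hypothesis, margin, power or precision target, so no stated claim fails. The draw is random within strata, and its size does not bias the estimates. SAP section 6.2.1 already tabulates the number in the MN per-protocol set by arm, so readers will see the actual size.

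The possible changes gain little:

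- Restating the size as 134 would write an inferred rate into the SAP.
- Drawing 177 per arm means up to 76 more participants assayed, with no stated target shown to be missed.
- Drawing only from participants who meet the per-protocol conditions would give up proportionality to the Full Analysis Set and delay the draw until exclusions are settled. It would also change a frame fixed in Protocol sections 9.3 and 9.4 and SAP sections 4.3, 5.5 and 6.3, or need an entry under SAP section 7, "CHANGES FROM PLANNED ANALYSIS IN PROTOCOL".

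The unexplained 5% is a detail that analysts can handle by reporting the number analysed. This conclusion rests on MN remaining descriptive and, for the CI factors, on the assumed SD of 1.0 to 1.5.
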